**In Vivo Evaluation of Antibacterial Toothpaste Efficiency and Patients' Satisfaction:
a Double-blind Randomised Controlled Trial**

NCT05569850

November, 20th 2024

Study Protocol

This was a single-site, double-blind RCT that was conducted in the Dental Clinic of Bologna University (DIBINEM), Bologna, Italy in the period from November 2022 until July 2023. Before initiating the trial, the study protocol was reviewed and approved by the University Ethics Committee (793/2022/SPER/AUSLBO). The trial was in accordance with Helsinki Declaration of Human Rights [21] and followed the CONSORT statement. The tested dentifrices included a newly introduced ZCT-, HAP- and KCit- 1450 ppm sodium monofluorophosphate containing (Experimental group; Mentadent PROTECT+ Carie, Mentadent, Unilever, Milan, Italy) and 1450 ppm NaF containing (Control group; AZ Multi-Protezione Scudo Protettivo Famiglia) toothpastes.

Sample size, recruitment and eligibility criteria

The number of patients was determined based on the power analysis performed using data from a previously published study in order to assure a power of 80% for finding the statistically significant differences given the standard value of type I errors (0.05). Based on the outcomes of the power calculation (effect size $f=0.2291667$, at the level of α 0.05, and $1-\beta$ prob 0.80), the determined sample size was 92 patients. Considering the probability of loss to follow-up 10% of the minimum size per group was added, leading to the final sample size of 100 patients.

Potential patients were recruited through local advertisement or on-site, during routine dental check-ups. Study details were explained to the potential participants and only those who voluntarily signed the informed consent were scheduled for the first visit. During the screening phase, one dentist evaluated the eligibility of the patients in the study based on the following inclusion criteria: male and female patients aged 18-50 with minimum of 20 natural teeth in stable occlusion and good oral hygiene level (bleeding on probing not exceeding 20%, no advanced periodontal disease, absence of active caries lesions, pulpitis), patients with good general health (no systemic diseases reported in the medical anamnesis), and subjects with good language comprehension. Exclusion criteria were tooth anomalies (i.e. amelogenesis imperfecta, dentinogenesis imperfecta etc.), intrinsic stain (i.e. fluorosis, molar incisors hypomineralization [MIH]), active caries lesions, advanced periodontal disease, smokers, presence of orthodontic devices, use of antibiotics in the last 3 months, use of antibacterial mouthrinses in the last 3 months, reported allergies, drug and alcohol addiction.

Study procedures

One week before the beginning of the trial, all patients received sub- and supra-gingival full-mouth prophylaxis. At the same appointment, patients were given detailed oral hygiene instructions by the dental hygienist and a brief explanatory video was shared via

messaging applications (i.e., WhatsApp) to serve as a reminder for good habits consulting during the study period. The patients were scheduled to come back after 7 days (baseline visit) and were asked not to brush or eat at least 5 hours before the appointment.

During the baseline visit, all patients completed a custom-made questionnaire (supplementary file) containing questions regarding dental sensitivity ("self-reported" sensitivity), their perception of tooth color and overall perception of the toothpaste they were using at the time. Subsequently, they were asked to collect 2 ml of unstimulated saliva in sterile tubes (Greiner centrifuge tube, Sigma-Aldrich, St Louis, MO, USA). Saliva was immediately processed for microbiological analysis as thereafter described. Upon saliva collection, a sensitivity test was conducted by applying a tactile and air-stimulus (duration: 2 s, distance from the tooth surface: 1 cm) test to all teeth of the four quadrants. The subjects' response was recorded on a 4-point Schiff Sensitivity Scale [25] and visual-analogue scale, respectively. Additionally, plaque index (Modified Quigley and Hein) was scored on a 6 point scale at 3 buccal and 3 lingual sites per tooth after it had been disclosed with a disclosing agent (Biofilm Disclosure, EMS Dental, Nyon, Switzerland); gingival index according to Löe-Silness was also recorded, as well as bleeding on probing index. Patients' tooth color was determined under daily light using the Vita classical shade guide. Finally, at the end of the baseline visit, the participants were provided with the same soft-bristled toothbrush (Mentadent P, Mentadent, Unilever) and randomly assigned into one of the two groups (n=50) according to the dentifrice used. An online software (<https://www.sealedenvelope.com>) was utilized for randomization purposes by a staff member unaware of the study protocol. In order to enable complete blinding of the participants and dental examiner to the group assignment, the two dentifrices were distributed in identical plain white tubes provided with only letters A or B, with no other visible marks. The patient's code and dentifrice assigned (A or B) were documented in the chart for later reference. From the baseline visit, the subjects had to restrain from using any other products or means of oral hygiene except those provided and were invited to follow the domiciliary oral hygiene instructions as previously described. In case of any adverse events were to occur, the subjects were advised to discontinue the use of the toothpaste and were withdrawn from the study. The 4 weeks follow-up visit was fixed (recall).

After 4 weeks (recall), the patients returned to the study site for a final visit after having abstained from brushing or eating at least 5 hours before the visit. During this visit, the patients were asked to fill in the questionnaire (supplementary file), while the saliva collection and all clinical procedures described above were repeated by the same dentist.

Microbiological procedures

The saliva collected during the baseline and recall visits was processed for microbiological analysis within 3 hours of sample acquisition. Briefly, 0.1 ml of saliva was diluted in 9.9 ml of sterile phosphate-buffered saline solution until 10^{-8} was reached. Subsequently, the diluted samples were dispersed on Mitis Salivarius Selective Agar (MSB, Microbiol Diagnostici, UTA, CA, Italy) and the plates were incubated at 37°C for the next 48-72h. The bacterial colonies were identified by morphology and counted by one trained investigator, blinded to the groups. *S. mutans* colonies (CFU) were multiplied by their respective dilution ratio to calculate the number of colonies per one milliliter

(CFU/mL) of each subject's saliva sample. In order to perform statistical analysis, a base-10 logarithm transformation was applied to the calculated CFU/ml values.

Statistical analysis

After checking the normality (Kolmogorov-Smirnov) and the homoscedasticity (modified Levene's test) of the data, the Two Way Repeated Measures ANOVA (One Factor Repetition) followed by Bonferroni post-hoc were run to investigate the effect of the tested dentifrices on salivary counts of *S. mutans*, as well as plaque and gingival indexes. Since the data retrieved from questionnaires were not normally distributed (Kolmogorov-Smirnov, $p<0.05$), the non-parametric Mann-Whitney U-test was run. All analyses were performed by a statistician blinded to the groups using SigmaPlot 14.0 (Systat Software, Chicago, IL, USA). In all tests, the significance level was set at $\alpha=0.05$.

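### Does the sample size of 92 contradict the stated effect size, alpha and 80% power?

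*Combined protocol and SAP*

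**What the plan says.** Under the heading on sample size, recruitment and eligibility, the document describes a "power analysis performed using data from a previously published study", carried out "in order to assure a power of 80% for finding the statistically significant differences given the standard value of type I errors (0.05". The inputs listed are f = 0.2291667, alpha 0.05 and power 0.80. From these "the determined sample size was 92 patients", raised to 100 for loss to follow-up.

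Under Study procedures, patients were "randomly assigned into one of the two groups (n=50) according to the dentifrice used". This was done at the end of the baseline visit, and there was one later assessment: "After 4 weeks (recall), the patients returned to the study site for a final visit". The design therefore has two arms and two measurements.

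Under Statistical analysis, "the Two Way Repeated Measures ANOVA (One Factor Repetition) followed by Bonferroni post-hoc were run to investigate the effect of the tested dentifrices" on salivary *S. mutans* counts, "as well as plaque and gingival indexes". The power calculation is not tied to any of these three outcomes or to a term of the ANOVA. No correlation between visits is given, and neither are the means and standard deviations behind f.

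**The concern.** A reader who puts the printed inputs into the simplest two-group calculation gets a total about 65% larger than the one stated (152/92 = 1.65). Taken at face value, the trial would then have had well under 60% power for the effect it names, while the text speaks of assuring 80%. A non-significant dentifrice comparison would be weaker evidence than the document suggests.

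The meaning of f is also open. Read as a two-group f, it is a difference of 2f = 0.458 SD. Read as the f of a group-by-visit interaction when the groups differ only at recall, it is a recall difference of 4f = 0.917 SD. The text does not say which effect the trial was sized to detect.

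**Working it through.** **Inputs from the document:** f = 0.2291667 (f² = 0.052517), alpha 0.05, target power 0.80, two equal groups, two visits, 92 patients before the loss allowance. **Assumed, because not given:** the correlation rho between visits, the ANOVA term and the scale of f. Power comes from the noncentral F distribution with 1 and N − 2 degrees of freedom. The required N is the smallest even total that reaches 80%.

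**1. Plain two-group comparison at one time point.** Noncentrality = f²N.
- N = 150 gives 79.6% and N = 152 gives 80.2%, so 152 are required.
- N = 92: 0.052517 × 92 = 4.83, power 58.5%.

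This does not reproduce 92, but it is not the planned analysis either.

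**2. Repeated measures ANOVA, between-group term, two visits.** Noncentrality = 2f²N/(1 + rho).

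| Assumed rho | N required | Power at 92 |
|---|---|---|
| 0 | 78 | 86.8% |
| 0.2 | 92 | 80.2% |
| 0.3 | 100 | 77.0% |
| 0.5 | 116 | 70.9% |

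At rho = 0.2 the noncentrality is 2 × 4.83/1.2 = 8.05. This reproduces the plan's figure exactly; any rho from about 0.18 to 0.20 does so.

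**3. Group-by-visit term, three scalings of f.**

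- *0.458 SD on the single-visit SD, present at recall only.* With d = 2f, noncentrality = d²N/[8(1 − rho)]. Power at 92 is 40.5%, 58.5% and 80.2% at rho 0.2, 0.5 and 0.7. N = 92 is returned at rho of about 0.70.
- *f on the interaction scale relative to the single-visit SD (0.917 SD at recall).* Noncentrality = 2f²N/(1 − rho). N required is 78, 62 and 40 at rho 0, 0.2 and 0.5; power at 92 is 86.8%, 93.0% and 99.2%.
- *f already expressed on the interaction's own error, correlation absorbed.* Noncentrality = f²N or f²(N − 2). N required is 152 or 154; power at 92 is about 58%.

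**4. Within-group change from baseline to recall,** one possible target of the Bonferroni comparisons. With n patients per group and n − 1 error degrees of freedom, noncentrality = nd²/[2(1 − rho)]. For n = 46 and rho = 0.415: 46 × 0.2101/1.17 = 8.26, power 80.3%. This gives 46 per group, again 92.

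**5. Low end.** If the between-group term is used but a 0.458 SD difference exists only at recall, noncentrality = f²N/[2(1 + rho)]. At rho = 0.2 this is 4.83/2.4 = 2.01, power about 29%.

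The printed inputs therefore do not fix N. Several readings that fit the two-arm, two-visit design return 92, and others need fewer or more patients.

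**The case for a change.** The strongest case for acting is that the document speaks of assuring 80% power yet leaves out inputs on which that figure depends. The reconstruction that lands on 92 most neatly, the between-group term at a correlation of 0.2, is itself undocumented. It also averages in a measurement taken before randomisation, when the toothpastes could not yet have acted; with an effect at recall only, its power is about 29%. The group-by-visit term at that same assumed correlation has 40.5% or 93.0% power, depending only on how f was scaled.

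Part of this stands. The calculation cannot be checked from the document, and a reader cannot tell whether 0.458 or 0.917 SD was the target.

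The rest does not carry. A repeated measures design can never be sized from f, alpha and the number of groups alone, so failure to get 92 from those three shows missing detail and not an error. The 80% is not free of conditions: the next sentence ties it to a stated effect size taken from earlier published data. Whether a visit-averaged term suits a dentifrice effect is a question about the choice of analysis, separate from whether 92 was computed correctly. Adding recalculated power figures would not help, since nearly all would rest on assumed correlations, and the 58.5% from the plain comparison could be mistaken for the trial's true power.

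**Conclusion.** No change is needed. The stated f, alpha and power with two groups give 152 only under a single-time-point comparison that the plan does not use. Under the planned two-visit ANOVA, 92 is attainable, for example with 80.2% power for the between-group term at an assumed correlation of 0.2. Across the readings examined, power at 92 runs from about 29% to 99%, and every value other than the plain benchmark of 58.5% and the own-error scaling of about 58% rests on a correlation the document does not give. That range shows that the 80% cannot be verified; it does not show that it is false.

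The gap is one of reporting. The trial ran from November 2022 to July 2023 and the document is dated November 2024, so the number enrolled is fixed. The ANOVA, its Bonferroni comparisons and the 0.05 level apply whichever inputs lay behind the 92. Naming the powered outcome, term, correlation and derivation of f would be a courtesy to readers, but would alter no enrolment, analysis or result.

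### Does the loss-to-follow-up allowance fall short because 100 patients is less than 92 plus 10%?

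*Combined protocol and SAP*

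**What the plan says.** Under the heading Sample size, recruitment and eligibility criteria, the combined protocol and SAP reports a power calculation ("effect size $f=0.2291667$, at the level of α 0.05, and $1-\beta$ prob 0.80") and concludes that "the determined sample size was 92 patients". It then allows for loss to follow-up: "10% of the minimum size per group was added, leading to the final sample size of 100 patients".

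The Study procedures section agrees with the final figure, since participants were "randomly assigned into one of the two groups (n=50) according to the dentifrice used".

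The document does not print the minimum per group, give a rounding rule, or say how many patients must remain evaluable after any given loss. It places the trial between November 2022 and July 2023.

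**The concern.** The stated percentage does not match the figures around it. Going from 92 to 100 adds 8.7%, not 10%. A reader who takes the sentence to mean that 10% loss is covered would be wrong by the plan's own numbers, because 10% loss from 100 leaves 90, two below the calculated minimum.

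If the shortfall were material, the trial could have fallen below its 80% power target at a loss rate it appeared to have provided for. A wrong inflation step can also be a sign that the wider sample size calculation was handled loosely, so it was reasonable to check it.

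**Working it through.** **Inputs.** From the sample size section: minimum 92, addition of 10% per group, final size 100, f = 0.2291667, alpha 0.05, power 0.80. From Study procedures: two groups of 50. The 46 per group is inferred from 92 / 2.

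**Reproducing the plan's figure**

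- Minimum per group: 92 / 2 = 46.
- Stated rule: 46 × 0.10 = 4.6, so 46 + 4.6 = 50.6 per group, or 101.2 in total.
- Fraction dropped: 50 per group, 100 in total. This matches both places in the document. The rounding down is inferred; the document does not describe it.
- Rounded up instead: 51 per group, 102 in total.

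**What was added and what it covers**

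- Addition: 4 / 46 = 8 / 92 = 8.7%.
- Loss that still leaves 92: (100 − 92) / 100 = 8%.
- Remaining at 10% loss: 100 × 0.9 = 90, which is 2 below 92.

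**Where the 2 patients come from**

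- Rounding: 101.2 × 0.9 = 91.08, and 91.08 − 90 = 1.08.
- Adding 10% instead of dividing by 0.9: 92 − 91.08 = 0.92. For comparison, 92 / 0.9 = 102.2.

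So the stated rule would not keep 92 at 10% loss even without rounding. Rounded up to 102, it leaves 102 × 0.9 = 91.8.

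**Effect on power of 90 instead of 92.** The document names neither the test nor the correlation between visits behind the 92, so these figures are illustrative. They use two groups, m = 2 visits, and F tests on 1 and N − 2 degrees of freedom.

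- Between-group test, λ = f² × N × m / (1 + (m − 1)ρ). With f² = 0.05252 and an assumed ρ = 0.2, chosen because it returns 92:
  - N = 92: λ = 0.05252 × 92 × 2 / 1.2 = 8.05, power 80.2%.
  - N = 90: λ = 0.05252 × 90 × 2 / 1.2 = 7.88, power 79.3%.
  - Difference: 0.9 points. Over assumed ρ from 0 to 0.9 the difference is 0.75 to 0.98 points.
- Group-by-visit interaction, λ = f² × N × m / (1 − ρ): the difference is 0.75 points at ρ = 0, 0.12 at ρ = 0.5 and below 0.01 at ρ = 0.7.
- Without choosing a correlation, take the noncentrality per patient that gives exactly 80.0% at 92. Power is then 79.1% at 90, 83.2% at 100 and 84.0% at 102.

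**The case for a change.** The best argument for a correction is that the contradiction needs no outside assumption: 92, 10% and 100 stand within two sentences and do not agree. Dropping the fraction explains how 100 arose, but it does not turn 8.7% into 10%. It also rounds in the unhelpful direction, since an allowance meant to protect a minimum is normally rounded up. The addition is explicitly tied to loss to follow-up, so a reader may well assume that 10% loss is covered. A corrected sentence would cost almost nothing.

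The mismatch and the unconventional rounding both stand. The shortfall against a minimum carries less weight. The plan says what was added; it does not undertake that 92 will remain after 10% loss. Of the 2 missing patients, about 0.9 come from adding a percentage where others would divide by the retention rate. The plan discloses that choice, so it is a matter of method, not an arithmetic error. What is left is about 1.1 patients, from dropping 0.6 patient in each group. A fraction of a patient cannot be enrolled, so some rounding was unavoidable.

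The low cost of rewording does not create a gain. Even the suggested correction would keep 100 patients and leave the design and the analysis as they are.

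**Conclusion.** No change to the plan follows. The stated 10% is really 8.7%, because 50.6 per group appears to have been cut to 50. This is a clerical rounding slip of 0.6 patient per group, 1.2 patients in total.

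Its practical effect is small and conditional. The 100 patients allow for 8% loss before fewer than 92 remain. At 10% loss, 90 instead of 92 evaluable patients would cost at most about 1 percentage point of power. The document reports no actual losses, so nothing shows that the 8% margin was used up. Recruitment and follow-up are complete, so no enrolment decision depends on the sentence, and no analysis, result or conclusion would change.

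This rests on equal groups (supported by the 50 per group), on the inferred rounding down, and on assumed tests and correlations for the power figures. It takes the 92 as given and does not confirm it. Anyone citing the allowance can describe it as about 9% added, which covers 8% loss.

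### Oral-hygiene products are not standardised in the week before baseline, so within-arm change is mixed with the product switch; the between-arm comparison stays unbiased in expectation

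*Combined protocol and SAP*

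**What the plan says.** Under Study procedures, the sequence is as follows.

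- **Seven days before baseline:** "One week before the beginning of the trial, all patients received sub- and supra-gingival full-mouth prophylaxis". Hygiene instructions and a reminder video are given at the same appointment. No toothpaste or brush is said to be supplied.
- **Between that appointment and baseline:** the only stated rule is that patients "were asked not to brush or eat at least 5 hours before the appointment".
- **Baseline visit:** patients complete a questionnaire that covers their "overall perception of the toothpaste they were using at the time". Saliva, sensitivity, plaque, gingival and bleeding measurements and tooth colour follow.
- **End of the baseline visit:** "Finally, at the end of the baseline visit, the participants were provided with the same soft-bristled toothbrush". Randomisation to a dentifrice takes place at the same point.
- **After that:** "From the baseline visit, the subjects had to restrain from using any other products or means of oral hygiene except those provided".

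Under Sample size, recruitment and eligibility criteria, the exclusions include "use of antibiotics in the last 3 months, use of antibacterial mouthrinses in the last 3 months". No toothpaste of any kind is listed.

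Under Statistical analysis, *S. mutans* counts and the plaque and gingival indexes go into a two-way repeated-measures ANOVA with Bonferroni post-hoc tests, so the baseline values are part of the analysed outcome.

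**The concern.** The eligibility rules treat an antibacterial rinse within three months as a reason to exclude, yet a daily user of an antibacterial toothpaste, the type of product named in the trial's title, can enter. Such a patient may use it until five hours before the baseline saliva sample. At the end of that visit every patient changes to the study brush and the assigned paste.

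The change from baseline to recall in either arm then has at least two sources: the assigned paste, and giving up whatever was used before. The second is common to both arms on average, so randomisation deals with it between arms but not within an arm. At stake are any statement that one dentifrice lowered or raised a score from baseline, and some precision in the group-by-time contrast. A week and an appointment that could have made baseline uniform are already in the schedule.

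**Working it through.** The plan gives no figure on this point, so there is nothing to reproduce. The check is a reading of the sequence, followed by an illustration under stated assumptions.

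**Reading.** The questionnaire item on the current toothpaste shows that patients come to baseline on a product of their own. That they also use their own brush follows from the study brush being issued only at the end of that visit. Allocation comes after all baseline measurements, so prior use cannot depend on the arm.

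**Inputs from the documents.** 50 patients per arm; two visits; log10-transformed *S. mutans* counts.

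**Assumed inputs, not in the documents.** SD 0.7 log10 at each visit among patients not on an antibacterial paste; baseline-recall correlation 0.6; a share *p* of patients whose usual paste lowers baseline by *δ* log10; that effect gone by recall.

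1. Variance of change without prior use: 2 × 0.7² × (1 − 0.6) = 0.392.
2. Variance added by mixed prior use: *p*(1 − *p*)*δ*². With *δ* = 0.5 this is 0.0225, 0.0525 and 0.0625 for *p* = 0.1, 0.3 and 0.5.
3. Divided by 0.392, the variance ratios are 1.057, 1.134 and 1.159. Their square roots give standard errors about 3%, 6% and 8% larger.
4. The same sum over a wider range, as rise in variance (rise in standard error):

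| *p* | *δ* = 0.3 | *δ* = 0.5 | *δ* = 1.0 |
|---|---|---|---|
| 0.1 | 2% (1%) | 6% (3%) | 23% (11%) |
| 0.3 | 5% (2%) | 13% (6%) | 54% (24%) |
| 0.5 | 6% (3%) | 16% (8%) | 64% (28%) |

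5. Shift of mean baseline, in both arms in expectation: *p* × *δ*. With *δ* = 0.5 this is 0.05, 0.15 and 0.25 log10. It enters the within-arm change in full and cancels, in expectation, between arms.
6. Chance imbalance between arms in the share of users, at *p* = 0.3: SD √(2 × 0.3 × 0.7 / 50) = 0.092, worth 0.092 × 0.5 = 0.046 log10. The standard error of the between-arm difference in change without prior use is √(2 × 0.392 / 50) = 0.125. Combined: √(0.125² + 0.046²) = 0.133, and (0.133/0.125)² ≈ 1.13. The imbalance is thus the 13% variance rise of step 3 in another form, not an additional harm.

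**The case against.** **The randomised comparison is protected.** A reader might infer bias between arms, since a prior user allocated to control loses an active agent while one allocated to the experimental paste swaps one for another. The documents do not support that. Such users fall into either arm by chance, and both arms get the same brush, restriction and follow-up. This objection stands.

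**Carry-over is possible, not shown.** A reader might take it as fact that baseline was measured under active treatment, or that the seven days were a failed washout. The documents do not report what patients used, never call the week a washout, and give no reason for the three-month exclusions. The content of the hygiene instructions is not shown either. This stands too.

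**The figures are assumed.** They run from 2% to 64% on the variance, and nothing in the documents narrows them. If an SD of 0.7 already describes patients on their own pastes, the variation is inside it, and a uniform run-in would gain precision rather than remove an excess. For the same reason the trial cannot be called underpowered: 92 × 1.134 = 104 exceeds the planned 100, but the plan does not state the effect or correlation behind 92, or whether its variance already includes mixed products.

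**A baseline under usual products is defensible.** Satisfaction is a titled aim, and the questionnaire deliberately asks about the current paste. This is a fair choice for those items, but they can be asked before a switch. It does not help the microbiological and clinical scores.

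**Excluding toothpaste users has a price.** Extending the mouthrinse exclusion to antibacterial pastes looks like the obvious remedy. At the assumed 10% to 50% use, enrolling 100 would need about 100/0.9 = 111 to 100/0.5 = 200 otherwise eligible candidates, from a narrower population. If few candidates use such pastes, there is little to gain. That exclusion is a trade-off, not a correction. Extending it to desensitising pastes has still less support: the figures above concern *S. mutans* only, and the ANOVA is not specified for the sensitivity scores.

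**Conclusion.** The point holds as a gap in standardisation. Products are uncontrolled in the week before baseline, and the change of brush and paste coincides with the start of treatment in both arms. Within-arm changes from baseline are confounded with that switch. The Statistical analysis section does not list the post-hoc pairs, but in this two-group, two-visit layout they ordinarily include baseline against recall within each arm. The group-by-time contrast may lose precision but is not biased in expectation.

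The size is unknown. In the central assumed case (SD 0.7, correlation 0.6, effect 0.5 log10, 10% to 50% use) the loss is 6% to 16% on the variance of change, or about 3% to 8% on the standard error: modest, and worth removing because removal is cheap. The confounding of within-arm change does not depend on those assumptions for its existence, only for its amount.

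**What to change.** **In a repeat or successor trial:** at the existing prophylaxis appointment, first ask the questionnaire items on the current toothpaste. Then hand out the study toothbrush and one common ordinary fluoride toothpaste, and start the restriction to supplied products there. No toothpaste exclusion need be added.

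The cost is about 100 extra tubes, with the brush and a few questionnaire items moved one week earlier. No visit, staff or procedure is added. The downside is that baseline no longer reflects patients' usual products.

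**For the data already collected** (the trial ran from November 2022 to July 2023):

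- Rest conclusions on the between-arm contrast.
- Report within-arm changes, including post-hoc comparisons between visits, as confounded by the switch of brush and paste.
- Adjust for habitual toothpaste type only if the questionnaire recorded it. The questionnaire is in a supplementary file that is not shown, so this may not be possible.

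This costs a sentence or two in the report and, if the data exist, one covariate.

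### Adverse events end study participation, so those affected have no 4-week values or product rating; if such withdrawals relate to outcome and differ between arms, the comparison can be biased, mainly for satisfaction

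*Combined protocol and SAP*

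**What the plan says.** All references are to the combined protocol and SAP.

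- **Study procedures, adverse events.** When an adverse event occurred, "the subjects were advised to discontinue the use of the toothpaste and were withdrawn from the study". No threshold of severity or causality is given. One sentence joins two separate acts: stopping the product and leaving the study.
- **Study procedures, allocation.** The order of events is that "at the end of the baseline visit, the participants were provided with the same soft-bristled toothbrush (Mentadent P, Mentadent, Unilever) and randomly assigned". Removal for an adverse event on the assigned product is therefore an exclusion after randomisation.
- **Study procedures, questionnaire.** The baseline questionnaire is completed before allocation and covers "overall perception of the toothpaste they were using at the time", that is, the participant's previous product. The questionnaire is completed again at recall. Its wording is in a supplementary file that is not part of the documents.
- **Study procedures, follow-up.** "After 4 weeks (recall), the patients returned to the study site for a final visit". No other assessment after baseline is described, and none at withdrawal.
- **Sample size, recruitment and eligibility criteria.** The only provision for loss is in the sample size: "Considering the probability of loss to follow-up 10% of the minimum size per group was added".
- **Statistical analysis.** S. mutans counts, plaque and gingival indexes go into a two-way repeated measures ANOVA. For the questionnaires, "the non-parametric Mann-Whitney U-test was run". No analysis population or missing-data method is named.

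**The concern.** A participant removed under this rule has a baseline value and nothing afterwards. With only two visits, that person contributes no observed change, so the time-by-product comparison rests in practice on those who remain. The same person never rates the assigned toothpaste, because recall is the only described occasion for doing so.

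The rule is identical in both arms, but what triggers it may depend on the product. If so, the rule removes people who reacted badly before they can say so. Randomisation and blinding do not repair this, because the selection happens after allocation. Patients' satisfaction is in the trial's title, and for that outcome the likely direction is clear: the less well tolerated product would look better. For the clinical outcomes the direction is unknown.

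**Working it through.** **The plan's own figure.** The sample size before loss is 92, or 46 per arm. Adding 10% per arm gives 46 × 1.10 = 50.6, rounded down to 50 per arm and 100 in total. The allowance is thus 4 per arm, 8 in total. It protects power but does not make those who remain comparable.

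**Inputs.** From the documents: 50 per arm and α = 0.05, taken here as two-sided. Assumed, because no adverse-event or withdrawal counts are given: k excess withdrawals in one arm, k = 1 to 5; withdrawn people differ from those who remain in that arm by 0.5 SD of the change, in either direction; no true difference between arms.

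**Clinical outcomes.** Bias in the difference of mean change = (k/50) × gap. In SD units, SE = √(1/50 + 1/(50 − k)). With r = bias/SE, the false-positive rate is Φ(−1.96 + r) + Φ(−1.96 − r), the same for either sign of the gap.

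| k | bias (SD) | SE (SD) | r | false-positive rate |
|---|---|---|---|---|
| 1 | 0.01 | 0.201 | 0.05 | 5.03% |
| 3 | 0.03 | 0.203 | 0.15 | 5.25% |
| 5 | 0.05 | 0.205 | 0.24 | 5.68% |
| 8 | 0.08 | 0.209 | 0.38 | 6.69% |

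The row k = 8 is an extreme: the whole allowance for both arms lost from one arm. The gap needed for a bias of 1 SE is 50 × SE/k, about 10 SD for k = 1 and about 2 SD for k = 5.

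Equal numbers do not guarantee safety. With 3 withdrawn per arm and gaps of +0.5 and −0.5 SD, the bias is 3/50 × 1.0 = 0.06 SD, SE = √(2/47) = 0.206, r = 0.29, and the rate is 5.97%.

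**Satisfaction.** Suppose the Mann-Whitney probability among completers is 0.50 (no difference). Let q be the chance that a withdrawn person would rank below a member of the other arm. With everyone included, the probability would be 0.5(1 − k/50) + (1 − q)k/50. Ignoring ties, SE = √(101/(12 × 50 × 50)) = 0.058.

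- q = 0.5 (withdrawn people answer like completers): 0.50, no bias.
- The same 0.5 SD gap as above gives q = Φ(0.5/√2) = 0.64: 0.497 (k = 1) to 0.486 (k = 5), at most 0.24 SE.
- q = 0.75 is a stronger assumption, a gap of about 0.95 SD: 0.495 to 0.475, or 0.09 to 0.43 SE.
- q = 1 (all withdrawn people ranked last), an upper bound: 0.49 to 0.45, or 0.17 to 0.86 SE.

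On an equal gap, satisfaction is affected no more than the clinical outcomes. It matters more because the direction is predictable and a larger gap is plausible: the reason for leaving bears directly on what is being rated.

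**The case against.** The best case against the point is that the conditions stack up. Adverse events must occur, withdrawals must differ between arms in number or type, and they must relate to the 4-week outcome. The documents report no adverse event. Participants are in good general health, people with reported allergies are excluded, and exposure is 4 weeks. Tubes are identical and the rule leaves no stated discretion. Large between-arm excesses are therefore unlikely, and for S. mutans, plaque and gingival indexes the figures are small. All of this stands and limits the weight of the point.

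An on-product question is also legitimate for a toothpaste. Following people who stopped yields some off-product values, and the plan says that "the subjects had to restrain from using any other products or means of oral hygiene except those provided". This too stands, as a downside of the fix.

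It does not make the point optional. The loss is not an accident of conduct but follows from the rule as written, and keeping these people to a visit that is already scheduled costs little.

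A reader might go further and infer that the trial's results are biased, or that unequal numbers alone would bias them. The documents support neither: they give no counts, and unequal numbers do no harm if withdrawn people would have answered like completers. A completer analysis is itself an inference from the two-visit design, since no analysis set is named.

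**Conclusion.** The concern holds as a conditional one. Read as written, the rule loses the 4-week clinical values and the product rating of anyone withdrawn for an adverse event, and the loss allowance addresses only power. Under the assumed 1 to 5 excess withdrawals and 0.5 SD gap, the effect on the clinical outcomes is probably small. For satisfaction it is equally small on the same gap, but it could approach 0.86 SE at the extreme, in favour of the less well tolerated product.

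There is no bias if no one was withdrawn this way, if those withdrawn would have answered like completers, or if withdrawals were alike in both arms. The documents do not show which case applies. Confidence is medium, because the counts are not given and the questionnaire was not available.

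**What to change.** **For further use of the protocol.** Leave the advice on stopping the toothpaste unchanged. Replace the clause that removes the participant from the study with continued follow-up to the scheduled 4-week recall, with the participant's agreement. Record which products were used after stopping, and analyse all randomised participants in their assigned arm. The cost is one changed sentence and no extra visit. Ethics approval and the participant's agreement are needed, because recall repeats saliva collection and all clinical procedures. The small downside is that the estimate then includes people who stopped the product.

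**For the completed trial.** Report adverse events and withdrawals, with reasons, by arm; the assigned letter is in each chart, so this is a count. If no one was withdrawn for an adverse event, nothing more is needed. If some were, keep the planned tests and add one simple sensitivity analysis of the satisfaction items over a range of assumed ranks for those withdrawn, from answering like completers to ranked last, with the last labelled as a bound. The small clinical figures do not justify an added imputation analysis. The missed 4-week data cannot be recovered.
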